3.11. Visit Windows

Once eligibility has been confirmed, the subject's Day 0 dose will be scheduled within 14 days after the next planned surgical intervention. If timing allows, the Day 0 dose may be given on the same day immediately following the next planned surgical intervention. Visit dates and windows must be calculated from Day 0, unless otherwise noted. All subjects will be followed until the Week 52 visit.

It is expected that all visits should occur according to the protocol schedule. All data will be tabulated per the scheduled visit as recorded on the case report form (CRF) even if the assessment is unscheduled (outside of the visit window). For example, a visit that occurs after the scheduled Week 6 visit, but before the scheduled Week 9 visit, will be reported (tabulated) with the Week 6 data. In data listings, the relative day of all dates will be presented.

3.12. Interim Analyses

No formal interim analyses are planned for this study. An analysis of the first 21 subjects [REDACTED] was conducted.

4. STUDY ANALYSES

4.1. Subject Disposition

Subject disposition will be tabulated by the number of prior surgeries, [REDACTED] and overall, for the number of eligible subjects, enrolled subjects, treated subjects, and subjects who completed study follow up visits through Week 52. In addition, the number of subjects who withdrew prior to completing the study and reason(s) for withdrawal will be tabulated.

The number of patients in each analysis population (ITT, mITT, PP, and SP) will be presented. Unless specified, percentages will be based on number of eligible subjects (i.e., ITT population).

By-subject data listings of study completion information, including reason(s) for premature study withdrawal, not participating, and inclusion/exclusion criteria not met, will be provided.

4.2. Demographics and Baseline Characteristics

Demographics, baseline characteristics, and medical history will be summarized by number of prior surgeries, [REDACTED] and overall. Age, height, weight, and BMI will be summarized using descriptive statistics (e.g., number, mean, standard deviation, median, minimum, and maximum). The number and percentage of subjects in each sex, race, and ethnicity category also will be presented. Childbearing potential and contraception method (when applicable) will be tabulated. Medical history, prior RRP treatment, and HPV type prior to study will be summarized. These tabulations will be presented on the mITT and safety populations. by MedDRA System Organ Class (SOC) and Preferred Term (PT) (v 25.0).

No formal statistical comparisons will be performed for these characteristics. All baseline data will be provided in by-subject listings.

4.3. Efficacy and Immunogenicity Evaluation

Efficacy and immunogenicity analyses will be conducted using the mITT Population. The Per Protocol population will provide supportive analyses.

The following efficacy evaluations will be conducted. Statistical methods and analysis of populations are described below.

4.3.1. Efficacy Analyses

The parameters that follow will be analyzed to support the conclusions of the primary analysis. For categorical endpoints, frequency and percentages will be calculated. For continuous variables, means, medians, or changes in percentage will be summarized. Where appropriate, 95% confidence intervals will be calculated (see specific analysis discussed subsequently). Analyses will be summarized and presented by number of prior surgical interventions (≤ 2 , 3-5, and ≥ 6), [REDACTED] and overall.

.

- Secondary analyses
 - Frequency of RRP surgical interventions in the year following intervention, compared to the frequency in the year prior will be presented as median difference with 95% CI based on non-parametric methodology.
 - Percent reduction in RRP surgical intervention as a categorical variable (categories consist of percent ranges), with frequency and percentages.
 - Change in surgical interval for prior to intervention to post will be presented along with median, mean, and 95% confidence intervals.
 - Change in stage as measured by the RRP Staging Assessment. Median changes and associated 95% confidence intervals will be computed.
 - The relationship of microRNA (miRNA) profiles with frequency of surgical intervention will be described using regression analysis.

■ [REDACTED]

■ [REDACTED]

■ [REDACTED]

In addition to these tabulations, by-subject listings will be provided for all efficacy endpoints.

4.3.2. Immunology Analyses

The following parameters will be presented:

- Secondary Immunogenicity Analyses
 - Cellular immune responses will be measured using ELISpot results from PBMCs. Median increase from baseline to each assessment point will be calculated along with associated 95% confidence intervals.
 - Immune response as determined by change in T cell phenotype and lytic markers measured using flow cytometry of PBMCs [REDACTED]. Median increases and associated 95% confidence intervals will be calculated.
 - Assessment of pro-inflammatory and immunosuppressive elements in resected tumor tissue [REDACTED]

[REDACTED]

[REDACTED]

[REDACTED]

4.4. Safety Analyses

Safety analyses will be conducted using the Safety Population, and will be tabulated by number of prior surgeries, [REDACTED] and overall. The primary analysis of this trial is the safety analysis of TEAEs, tolerability, and change in safety lab parameters.

4.4.1. Study Drug Exposure

Study drug exposure will be tabulated by the number of doses received and presented by number of prior surgeries, [REDACTED] and overall.

The location of the EP injection, guide usage, and whether there was a second EP attempt will also be summarized. Study drug exposure for each subject will also be presented in a data listing.

4.4.2. Adverse Events

All adverse events (AEs) will be coded using the MedDRA coding system (v. 25.0 or higher) and displayed in tables and data listings by SOC and PT. AEs will be summarized for the safety population by number of prior surgeries, [REDACTED] and overall. Tables will describe the incidence of AEs. In these tabulations, each subject will contribute only once (i.e., the most related occurrence or the most intense occurrence) to each of the incidences in the analysis, regardless of the number of episodes. Multiple occurrences of the same AE will be counted only once following a worst-case approach with respect to severity and relationship to study treatment.

Adverse events with onset after the administration of study medication through 30 days following the last dose, are considered treatment emergent adverse events (TEAEs). The frequency and 95% Clopper-Pearson CIs of TEAEs will be calculated. An overall summary of TEAEs will include the number and percentage of subjects with any TEAE, any TEAE assessed by the Investigator as related to treatment, any TEAE by severity grade, any SAE, any pre-treatment AE, any AE leading to discontinuation of treatment, and any AE leading to death and separately for events occurring within 7 days of any dose and regardless of when they occurred. AEs and SAEs that are not TEAEs or serious TEAEs will be presented in listings:

- All TEAEs
- All TEAEs by most recent dose*
- All TEAEs by severity grade
- All TEAE considered treatment-related
- All TEAEs by most recent dose and severity grade *
- All AEs that occur any time within 52 Weeks on Study
- All treatment related TEAEs by most recent dose *

*TEAEs of this type will also be presented within 7 days.

All adverse events occurring on-study will be provided in by-subject data listings along with subject deaths, SAEs, Grade 3/4 level events and DLTs, and AEs leading to withdrawal.

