7.2 ADVERSE EVENTS (AEs)

Any untoward medical occurrence in a patient or clinical investigation subject administered a pharmaceutical product and which does not necessarily have to have a causal relationship with this treatment.

An AE can therefore be any unfavorable and unintended sign (including an abnormal laboratory finding, for example), symptom, or disease temporally associated with the use of a medicinal product, whether or not considered related to the medicinal product.

Adverse Events (AEs) include the following:

- Pre- or post-treatment complications that occur as a result of protocol mandated procedure during or after screening (before the administration of clinical trial drug)
- Any pre-existing condition, with the exception of the condition under investigation in this study, that increases in severity, or changes in nature during or as a consequence of the clinical trial drug administration phase
- Complications of pregnancy (refer to [section 7.11: Reporting Pregnancy During the Clinical Trial](#))

Adverse Events (AEs) do not include the following:

- Medical or surgical procedures (e.g., surgery, endoscopy, tooth extraction, transfusion) performed; however, the condition that leads to the procedure is an AE
- Pre-existing diseases or conditions or laboratory abnormalities present or detected before the Screening Visit that do not worsen
- Recurrences of RRP (disease under study)
- Situations where an untoward medical occurrence has not occurred (e.g., hospitalization for elective surgery, social and/or convenience admissions)
- Overdose without clinical sequelae
- Any medical condition or clinically significant laboratory abnormality with an onset date before the ICF is signed, is not an AE; it is considered to be pre-existing and will be documented on the medical history CRF
- Uncomplicated pregnancy
- An induced elective abortion to terminate a pregnancy without medical reason

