7.9 SAFETY DATA REPORTING PERIOD, METHOD OF COLLECTION AND SUBMISSION

All AEs will be collected from the time when informed consent is obtained to Week 52 or at participant's last visit due to early discontinuation. This information will be captured in the Electronic Data Capture (EDC) system.

If the PI determines that the AE meets serious criteria, then the AE will be recorded as an SAE.

SAEs and DLTs will be reported to the Sponsor from the time the subject signs the informed consent until Week 52 or at participant's last visit due to early discontinuation.

All SAEs (regardless of causal relationship) and DLTs, will be reported on the SAE Report Form and submitted to the Sponsor within 24 hours of becoming aware of the event.

The original SAE Report Form must be kept at the clinical trial site.

The event will be data entered into the EDC.

For the events that are considered a DLT, the PI will contact the Sponsor within 24 hours of becoming aware of the event to discuss whether dosing should continue.

SAE Contact Information

Safety Email:	
Safety Fax:	
Safety Phone:	

Medical Monitor Direct contact Information

Medical Monitor:		M.D.
Email:		
Cell Phone:		

All SAEs, and DLTs must be followed by the PI until resolution or return to baseline status, or stabilization of the event (i.e., the expectation that it will remain chronic), even if it extends beyond the clinical trial reporting period.

Follow-up information is to be submitted to the Sponsor on an SAE Report Form and within 24 hours of becoming aware of the information.

If medical records are submitted to the Sponsor with the SAE Report Form, the clinical trial site must:

- Redact the medical records of all personal data (e.g., confidential subject data, Personal Identifying Information (PII))
- Provide the assigned clinical trial subject number (SID) on the records

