8.5 DESCRIPTION OF STATISTICAL METHODS

8.5.1 Primary Analyses

The primary analyses for this trial are safety analyses of Treatment Emergent Adverse Events (TEAE) and clinically significant changes in safety laboratory parameters from baseline.

TEAEs are defined for this trial as any AEs that occur following Day 0 following administration of study drug (IM + EP), until 30 days following the last dose. All TEAEs will be summarized among the Safety Population by frequency. These frequencies will be presented overall, by system organ class and by preferred term, the percentage of subjects affected. Additional frequencies will be presented with respect to maximum severity and to strongest relationship to study treatment. Multiple occurrences of the same

AE will be counted only once following a worst-case approach with respect to severity and relationship to study treatment. All serious TEAEs will also be summarized as above.

The main summary of safety data will be based on TEAEs. For this summary, the frequency of preferred term events will be calculated along with 95% confidence intervals, using the exact method of Clopper-Pearson. Separate summaries will be based on events occurring within 7 days of any dose and regardless of when they occurred. AEs and SAEs that are not TEAEs or serious TEAEs will be presented in listings.

For AE data, partial start dates will be imputed to the date of treatment to conservatively report the event as treatment-emergent, whenever the portion of the date is consistent with that of the study treatment. Otherwise, it will be imputed to the earliest date consistent with the partial date. A completely missing onset date will be imputed as the day of treatment. Partial stop dates will be assumed to be the latest possible day consistent with the partial date.

AE duration will be calculated as (Stop Date – Start Date) + 1.

Laboratory response variables will be descriptively summarized per time point and as changes from baseline including 95% confidence intervals. Shifts from baseline according to the CTCAE will also be presented. Laboratory values considered clinically significant will be presented in listings.

All of the safety analyses will be conducted on the subjects in the safety analysis set.

Analyses will be summarized and presented by number of prior surgical interventions (≤ 2 , 3-5, and ≥ 6) and overall.

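### The TEAE definition has no worsening clause, so a screening-onset AE that worsens after dosing may be missed from the TEAE tables, depending on how the site records it

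*SAP*

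**What the plan says.** **Definition.** SAP 4.4.2 states: "Adverse events with onset after the administration of study medication through 30 days following the last dose, are considered treatment emergent adverse events". Protocol 8.5.1 takes TEAEs to be "any AEs that occur following Day 0 following administration of study drug (IM + EP), until 30 days following the last dose". Neither adds AEs that were present before dosing and worsen after it.

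**Role.** Protocol 8.5.1: "The main summary of safety data will be based on TEAEs". SAP 4.4: "The primary analysis of this trial is the safety analysis of TEAEs, tolerability, and change in safety lab parameters". SAP 4.4.2 plans outputs by severity grade, by relationship to treatment, by most recent dose and within 7 days of a dose, all built on TEAEs. For the rest, both documents use the same sentence: "AEs and SAEs that are not TEAEs or serious TEAEs will be presented in listings".

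**Collection.** Protocol 7.9: "All AEs will be collected from the time when informed consent is obtained to Week 52" or to the last visit after early discontinuation. Section 6.1.1 allows screening up to 60 days before Day 0. Section 3.0 places papilloma removal within 14 days before Day 0, same day allowed. Section 7.2 counts complications of protocol-mandated procedures as AEs even before study drug.

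**Worsening.** Protocol 6.1.1.1 requires worsening of an existing illness after consent to be documented as an AE. Section 7.2 lists as an AE "Any pre-existing condition, with the exception of the condition under investigation in this study, that increases in severity, or changes in nature" in the drug administration phase. Of a condition with onset before consent is signed, the same section says "it is considered to be pre-existing and will be documented on the medical history CRF".

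**The concern.** Treatment emergence normally covers two situations: an event that starts after dosing, and an event already present that becomes worse after dosing. Both definitions here state only the first.

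The gap is relevant to this design because subjects can have AEs open at Day 0. AE collection starts at consent, and every subject has an operation before the first dose. Suppose an AE begins in screening at Grade 1 and rises to Grade 3 after the first dose. If it stays on its original record, its onset is before dosing and it fails the definition. It would then be absent from the TEAE tables by severity and relatedness, although the change happened on treatment. Two sites could record the same course differently and give opposite classifications in the primary safety analysis.

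**Working it through.** **1. What decides TEAE status.** The SAP uses onset; the protocol uses occurrence after study drug. SAP 3.10 gives partial-date rules for settling treatment emergence, and they act on the onset date alone. Grade changes play no part. The same rules push doubtful dates towards counting the event as treatment-emergent, so omitting worsening does not match the plan's own conservative intent.

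**2. Whether the recording rules close the gap.**

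| Place | What it settles | What it leaves open |
|---|---|---|
| Protocol 6.1.1.1 | Worsening of an existing illness after consent is an AE | Whether an AE already on the CRF gets a second record; which onset date applies |
| Protocol 7.2 | A pre-existing condition that worsens in the dosing phase is an AE | Whether a condition starting between consent and Day 0 is pre-existing; which onset date applies |
| Protocol 7.8.2 | A laboratory abnormality that worsens from baseline and meets a listed criterion is an AE | Which onset date applies; non-laboratory events |
| Protocol 6.1.2 | New AEs are collected after dosing; present, new or ongoing AEs at visits | Whether an ongoing AE with a higher grade is a new entry |

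None of these places gives a worsened open AE a new record or onset date.

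**3. The two possible outcomes.**

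- *New record, dated at the worsening.* Onset is after dosing, so the event is a TEAE if it falls within 30 days of the last dose.
- *Original record kept, grade raised.* Onset is before dosing, so the event is not a TEAE. It may still be counted under any SAE or any pre-treatment AE in the SAP's overall summary. It would also be in the all-AE summaries and the listings. Laboratory worsening would appear in the CTCAE grade shifts (SAP 4.4.3).

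**4. Reproducing the plan's own safety figure.** SAP 3.1 gives a true SAE incidence below 12% for n = 30 if no additional SAEs are seen. With the exact two-sided 95% method that the plan names, the upper limit for 0/30 is 1 − 0.025^(1/30) = 11.57%, which agrees. A one-sided 95% limit would be 1 − 0.05^(1/30) = 9.50%, and the rule of three gives 3/30 = 10.0%. This figure is not in dispute.

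**5. Illustration of size.** The documents give no count of screening AEs that worsen. Assume n = 30 and one preferred term with no other cases. Exact (Clopper-Pearson) 95% limits:

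- 0/30: 0%; upper limit 11.6% as above.
- 1/30: 1/30 = 3.3%. Lower limit 1 − 0.975^(1/30) = 0.08%. The upper limit solves (1 − p)^30 + 30p(1 − p)^29 = 0.025, giving 17.22%. Interval 0.1 to 17.2%.
- 2/30: 2/30 = 6.7%; interval 0.8 to 22.1%.

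Omitting one such subject reports 0/30 (0 to 11.6%) in place of 1/30 (3.3%, 0.1 to 17.2%). Omitting two reports 0/30 in place of 2/30. Zero, one or two is an assumed range, not an estimate.

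**The case against.** The best reply is that the protocol already makes worsening an AE. Section 6.1.1.1 is not limited to illnesses that began before consent. Section 7.2 says that a condition with onset before consent is pre-existing, but not that only such conditions are; another bullet there refers to the Screening Visit, and the worsening bullet to the drug administration phase. A site could fairly read these together as requiring a new AE dated at the worsening, which would then be a TEAE. The table shells listed in the SAP's revision history, and any CRF completion instructions, were not available and might settle the matter.

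Much of this stands. A reader might infer that every such event is certainly left out of the primary safety tables, or would appear only in listings. The documents support neither. Omission depends on site recording, and SAP 4.4.2 counts any SAE and any pre-treatment AE in the overall summary. Protocol 8.5.1 plans a summary regardless of timing, and the SAP plans an output of all AEs over 52 weeks (its lead-in leaves table or listing unclear). A reader might also infer that the operation makes pre-dose AEs common; no rate is given.

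What the reply does not do is supply a dating rule. The other outputs would show the original event, but not as a post-dose worsening, and the pre-treatment row would place it before treatment. The grade shifts cover laboratory parameters only.

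**Conclusion.** The concern holds in conditional form. Both TEAE definitions lack a worsening clause, and no available text says how a screening-onset AE that worsens after dosing is dated. Where the original record and pre-dose onset are kept, the worsening is missed from the TEAE tables, including those by severity, relatedness, most recent dose and 7-day window.

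The size cannot be computed from the documents. The step from 1/30 to 0/30 for a preferred term with no other cases rests on an assumed single omitted subject. It shows only that, at n = 30, individual subjects change a reported rate visibly.

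The issue is one of reporting. The DLT definition and the rules for pausing enrollment and dosing do not use TEAE status. The analysis is descriptive, with no formal hypothesis (protocol 8.3), so no decision threshold is affected.

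**What to change.** In protocol 8.5.1 and SAP 4.4.2, define a TEAE as an AE with onset after the first dose, or an AE with onset before the first dose that increases in severity or becomes serious after the first dose, through 30 days after the last dose.

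State that such a worsening is recorded as a new AE, dated at the worsening and linked to the original record.

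If data are already collected, review all screening-onset AEs ongoing at Day 0, and establish the date of any post-dose grade change before the tables are finalised. This is likely to be needed: SAP 3.12 describes an analysis of the first 21 subjects as already done.

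The cost is a short change in each document, one derivation and a limited data check. TEAE counts may rise slightly.

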4.4.3. Laboratory Data

Clinical laboratory values will be expressed in SI units. Laboratory values will be summarized for each clinical laboratory parameter, including hematology and serum chemistry. For women of childbearing potential, a serum pregnancy test will be assessed at screening, and urine pregnancy tests prior to each dose administration.

The mean change from baseline and corresponding 95% CI, and shifts in CTCAE grade, to each on-study evaluation will be summarized for each clinical laboratory parameter.

All laboratory data will be provided in data listings. A subset listing will be presented for all clinically significant laboratory values.

4.4.4. Vital Signs and Physical Examination

Vital sign values as well as changes from baseline (shift table) will be summarized by scheduled visit for subjects in the safety population. Descriptive statistics will be tabulated by number of prior surgeries, [REDACTED] and overall. Vital sign measurements will be presented for each subject in a data listing.

Physical examinations performed will be summarized in tables by scheduled visit. Reasons for physical examinations not done will be presented in a data listing.

4.4.5. Prior and Concomitant Medications and Procedures

Prior medications and/or procedures are those used or performed before the start of trial, i.e. before Day 0 dosing. Concomitant medications and/or procedures are those used or performed during the trial (on or after the first dose). Concomitant medications also include any that did not end prior to first dose of the study treatment, are missing an end date, or are ongoing, and will be included. Concomitant procedures, defined as continuing or new procedures and treatments undergone by the subject at or after first (Day 0) dosing, will be included.

Partial stop dates of concomitant medications and procedures will be assumed to be the latest possible date consistent with the partial date; start dates will not be imputed. Data for all concomitant medications will be summarized with counts and percentages by WHO Drug Anatomical Therapeutic Chemical (ATC) classification and preferred term, for the mITT population. The use of concomitant medications and procedures will be presented in a by-subject data listing.

